A serious adverse event is an AE occurring during any study phase (i.e., screening, run- in, treatment, wash-out, follow-up), at any dose of the study drugs that fulfills one or more of the following criteria and deemed secondary to the use of study drug:

- Results in death
- Is immediately life-threatening
- > Requires in-patient hospitalization or prolongation of existing hospitalization
- Results in persistent or significant disability or incapacity
- > Is a congenital abnormality or birth defect
- Is an important medical event that may jeopardize the patient or may require medical intervention to prevent one of the outcomes listed above.
- 1.1.1 The causality of SAEs (their relationship to all study treatment/procedures) will be assessed by the investigator(s) and communicated to Boehringer Ingelheim (BI) via BI SAE form and the FDA via MedWatch form, if applicable.

Causality will be reported as either "Yes" or "No".

- Yes: There is a reasonable causal relationship between the investigational product administered and the AE.
- ➤ No: There is no reasonable causal relationship between the investigational product administered and the AE.

2. Recording of Adverse Events

Rutgers, The State University of New Jersey [name]

Non-serious adverse events and SAEs will be determined from the time the patient is enrolled into the study and up to and including the 2 weeks follow-up period (after the completion of 2 weeks of treatment with Aggrenox) for a total of 28 days . All grade 3 or higher AEs will be recorded. Grade 1-2 AEs do not need to be recorded. After withdrawal from treatment, subjects must be followed-up for all existing and new AEs for 14 calendar days after the last dose of trial drug and/or until event resolution. All new AEs occurring during that period must be recorded (if SAEs, they must be reported to the DSMB and Rutgers IRB as per SOPs.). AEs will be recorded per Rutgers IRB SOPs. The common terminology criteria for adverse events (CTCAE) will be used as a reference to grade the adverse events.

(https://ctep.cancer.gov/protocoldevelopment/electronic_applications/docs/CTCAE_v5_Quick_R eference_8.5x11.pdf (Accessed on March 09, 2018)

All study-related adverse events/ SAEs must be followed until resolution, unless in the Treating Investigator's opinion, the condition is unlikely to resolve due to the patient's underlying disease.

3. Reporting of Serious Adverse Events

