Investigators and other site personnel must inform the Rutgers IRB per the SOPs on the required forms. FDA will be informed per SOP, via a MedWatch, of any serious or unexpected adverse events that occur in accordance with the reporting obligations of 21 CFR 312.32. It is the responsibility of the principal investigator to compile all necessary information and ensure that the FDA receives a report according to the FDA reporting requirement timelines.

In addition to FDA, the Sponsor shall report all SAEs and non-serious AEs that occur ,throughout the treatment period and up to and including the 2 weeks follow-up period (after the completion of 2 weeks of treatment with Aggrenox) for a total of 28 days which are relevant for a reported SAEs and any AEs relevant to a reported SAE by fax or other secure method using BI IIS SAE form to the BI Unique Entry Point in accordance with timeline specified in the safety data exchange agreement .

For each adverse event, the investigator will provide the onset date, end date, causality, intensity, treatment required, outcome, seriousness, and action taken with the investigational drug.

The investigator does not need to actively monitor patients for adverse events once the clinical trial has ended. However, if the investigator becomes aware of an SAE(s) that occurred after the patient has completed the clinical trial (including any protocol specified follow-up period), it should be reported to BI if investigator considers it as relevant to the BI study drug.

All SAEs meeting the criteria for expedited reporting will be reported to the Rutgers IRB within the mandated time frames. All SAEs within the safety follow-up window (e.g., within 14 days after the last dose of study medications) established in the protocol will be reported.

Non-serious adverse events and SAEs will be collected from the time the patient is enrolled into the study, throughout the treatment period and up to and including the 2 weeks follow-up period (after the completion of 2 weeks of treatment with Aggrenox) for a total of 28 days. After withdrawal from treatment, subjects must be followed-up for all existing and new AEs for 14 calendar days after the last dose of trial drug and/or until event resolution. All new AEs

Protocol Title: ATTAC-19 – Aggrenox To Treat Acute Covid-19 Pro#2020001469

Rutgers, The State University of New Jersey [name]

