occurring during that period must be recorded (if SAEs, then they must be reported to the FDA as per their reporting criteria). All study-related toxicities/ SAEs must be followed until resolution, unless in the Treating Investigator's opinion, the condition is unlikely to resolve due to the patient's underlying disease.

Clinical Safety Assessments

Recording of Adverse Events

Non-serious adverse events and SAEs will be determined from the time the study drug is given, throughout the treatment period and up to and including the 2 weeks follow up period. All grade 3 or higher AEs will be recorded. Grade 1-2 AEs do not need to be recorded. After withdrawal from treatment, subjects must be followed-up for all existing and new AEs for 14 calendar days after the last dose of trial drug and/or until event resolution. All new AEs occurring during that period must be recorded (if SAEs, they must be reported to the DSMB and Rutgers IRB as per SOPs.). AEs will be recorded per Rutgers IRB SOPs.

Adverse Events Based on Signs and Symptoms

When collecting AEs, the recording of diagnoses is preferred (when possible) to recording a list of signs and symptoms. However, if a diagnosis is known and there are other signs or symptoms that are not generally part of the diagnosis, the diagnosis and each sign or symptom will be recorded separately.

Vital Signs

Temperature will be obtained at least two times a day (AM and PM). Nursing staff will record the temperature while the patient is in the hospital. Body temperature will be measured in degrees Fahrenheit using an automated thermometer. An automated thermometer will be provided to the patient once discharged from the hospital for checking the temperature at least once a day for the study duration (28 days total from the enrollment day).

Study Efficacy/Response Assessments

Change in composite COVID ordinal scale at day 15. Ordinal scale: 1) not hospitalized with resumption of normal activities; 2) not hospitalized, but unable to resume normal activities; 3) hospitalized, not requiring oxygen; 4) hospitalized, requiring oxygen; 5) hospitalized, requiring high-flow oxygen therapy, or noninvasive ventilation; 6) hospitalized, requiring invasive ventilation; 7) ventilation plus additional organ support such as pressors, renal replacement therapy and ECMO and 8) death.

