1.6 Study Variables

A. Independent Variables, Interventions, or Predictor Variables

The following variables will be examined for treatment outcomes of efficacy and/or predict outcomes:

- Treatment
- Baseline temperature
- Baseline SARS-CoV test
- Baseline measure of inflammatory markers

B. Dependent Variables or Outcome Measures

The following variables will be examined for changed as result of treatment or as predictors

- Treatment Compliance
- Change in the fever curve
- Improvement in vital signs
- Time to discharge (if hospitalized)
- Adverse Events (number/percentage/grade)
- Inpatient versus Outpatient
- Change from baseline SARS-CoV test
- Change from baseline inflammatory markers

RUTGERS | eIRB APPROVED

Approval Date:

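### The protocol states the adverse-event grade threshold inconsistently, and one version, if read as all grades, makes low-grade recording compulsory only for Aggrenox patients who stop treatment

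*Combined protocol and SAP*

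**What the plan says.** Section 1.2 (Research Design and Methods) describes AE recording in three places.

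- **Recording of Adverse Events, under Study Safety Assessments.** The period runs from enrolment for 28 days in total. The threshold is "All grade 3 or higher AEs will be recorded. Grade 1-2 AEs do not need to be recorded". The paragraph then turns to patients withdrawn from treatment, who are to be followed "for all existing and new AEs for 14 calendar days after the last dose of trial drug and/or until event resolution", and adds "All new AEs occurring during that period must be recorded".
- **Reporting of Serious Adverse Events.** "Non-serious adverse events and SAEs will be collected from the time the patient is enrolled into the study, throughout the treatment period" and on to day 28. No grade is mentioned. The post-withdrawal duty to record all new AEs is repeated, again with no grade sentence beside it.
- **Recording of Adverse Events, under Clinical Safety Assessments.** The grade 3 rule is repeated, followed by the same post-withdrawal sentences. The start differs: "Non-serious adverse events and SAEs will be determined from the time the study drug is given".

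The comparator arm receives standard care only, and the trial is open-label. Section 1.6 (Study Variables, part B) lists AEs by number, percentage and grade among the outcome measures, with no grade cut-off ("Adverse Events (number/percentage/grade"). AEs as such are not a primary or secondary endpoint, and sections 1.5 and 6.1 name no AE analysis.

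**The concern.** A between-arm AE summary is interpretable only if the same events are eligible for recording in both arms. Here the stated threshold varies by paragraph, and one version depends on treatment status. The post-withdrawal window is counted from the last dose of trial drug, a date that no standard-care patient has. If site staff take that sentence to mean every grade, a low-grade event must be recorded in an Aggrenox patient who has stopped. The same event need not be recorded in a control patient, or in an Aggrenox patient still on treatment.

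At stake is the descriptive safety comparison. More Aggrenox patients could appear with an AE through the recording rule alone, and the grade distribution could shift because low-grade entries would come mainly from patients who stopped. In an open-label trial, where lower-grade recording is otherwise discretionary, such an imbalance would be hard to tell from a real effect. Low-grade events never recorded for controls may not be recoverable afterwards.

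**Working it through.** The plan gives no AE rate or AE calculation to reproduce. The check is a comparison of the three statements, then an illustration of size.

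**Step 1: the statements side by side (all in section 1.2)**

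| Place | General threshold | Post-withdrawal duty | Can it operate in the control arm? |
|---|---|---|---|
| Recording of Adverse Events (Study Safety Assessments) | Grade 3+ recorded, grade 1-2 optional | All new AEs, no grade | General rule yes; post-withdrawal duty no |
| Reporting of Serious Adverse Events | None stated | All new AEs, no grade | Collection sentence yes, as it starts at enrolment; post-withdrawal duty no |
| Recording of Adverse Events (Clinical Safety Assessments) | Grade 3+ recorded, grade 1-2 optional | All new AEs, no grade | Start is tied to study drug; post-withdrawal duty no |

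Two things follow from the text alone. The threshold is inconsistent, and the duty counted from the last dose can be applied in only one arm. The collection sentence without a grade limit supports the first conclusion but not the second.

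**Step 2: how large the effect could be**

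Assume no true difference between arms, and let:

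- p = proportion of patients with a grade 3+ AE, 20% to 40% in both arms (assumed);
- w = proportion of Aggrenox patients who stop early, 5% to 25% (assumed). The upper end is the 25% discontinuation for AEs that section 4.7 reports for Aggrenox in the stroke prevention study, used as a bound and not as a forecast for 14 days;
- q = chance that a patient who stopped has a new grade 1-2 AE in the window, 30% to 60% (assumed, independent of p and w).

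If the post-withdrawal sentence means all grades and all recorded grades are pooled, the recorded proportions are:

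- control: p
- Aggrenox: p + (1 − p) × w × q

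The spurious excess is (1 − p) × w × q.

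| Stopping w | Smallest excess (p = 0.4, q = 0.3) | Largest excess (p = 0.2, q = 0.6) |
|---|---|---|
| 5% | 0.6 × 0.05 × 0.3 = 0.9 points | 0.8 × 0.05 × 0.6 = 2.4 points |
| 10% | 0.6 × 0.10 × 0.3 = 1.8 points | 0.8 × 0.10 × 0.6 = 4.8 points |
| 25% | 0.6 × 0.25 × 0.3 = 4.5 points | 0.8 × 0.25 × 0.6 = 12.0 points |

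The corresponding risk ratios run from 0.409/0.40 = 1.02 to 0.32/0.20 = 1.60. With 66 patients per arm (section 1.5), 0.9 points is 0.6 of a patient and 12 points is 7.9 patients. With q as low as 10%, the smallest excess at 5% stopping is 0.6 × 0.05 × 0.1 = 0.3 points.

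**Step 3: if someone tested the difference**

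The plan contains no such test, so this is illustrative only. Take p = 30%, 66 per arm, and a pooled z-test with exact binomial enumeration. The chance of z > 1.96 against Aggrenox is about 2.5% with no excess, 4.5% to 7.5% at w = 10%, and 9.5% to 25% at w = 25% (q = 0.3 and 0.6 respectively).

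**Step 4: after the fix**

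With one threshold and one window in both arms, the excess created by the recording rule is zero by construction.

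**The case against.** The best reply is that the post-withdrawal sentences only extend the observation period under the threshold set just before them. In the two paragraphs that state the grade 3 rule, the sentence order allows that reading, and the excess is then zero. Those paragraphs also defer to institutional procedures that are not in the documents. This stands as a possible reading but not a secure one. Under Reporting of Serious Adverse Events the same duty appears with no grade sentence near it, and elsewhere the wording moves from optional to compulsory within one paragraph.

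A second reply is that the problem can be repaired at analysis. Events are graded by CTCAE and intensity is collected for each AE, so a grade 3+ table would drop the surplus. That is right, but the plan does not specify such a table, and section 1.6 lists AEs by grade without a cut-off.

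Several stronger readings are tempting, and the documents do not support them:

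- *Aggrenox AE counts will be inflated.* This needs the all-grades reading, patients who stop, new low-grade events after stopping, and a summary that pools grades.
- *Every statement without a grade limit applies to Aggrenox alone.* The collection sentence starts at enrolment and can cover both arms. If it governs, all grades are collected in everyone.
- *Controls have only grade 3+ events recorded.* Lower grades are optional ("Grade 1-2 AEs do not need to be recorded"), not barred, in either arm.
- *Every Aggrenox patient enters the all-grade window at day 14.* That would mean about 4 to 26 extra patients of 66 (p = 20% to 40%, q = 10% to 50%), but it counts completion as withdrawal, and the protocol names completion separately.
- *The trial's error rate is affected.* No AE hypothesis, test or alpha is specified, and the general sentence on risk ratios for binary outcomes names no AE outcome.

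**Conclusion.** The point holds in a limited form. Section 1.2 conflicts with itself on which AE grades are recorded, and the post-withdrawal rule can operate only in the Aggrenox arm. Read as all grades, it makes low-grade recording compulsory only for Aggrenox patients who stop, and it could inflate that arm's AE number, percentage and grade summary.

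The documents do not fix the size. It is nil if grade 3+ governs throughout or the summary is restricted to grade 3+. It is about 1 to 2 percentage points at 5% stopping, given the assumed 20% to 40% base rate and 30% to 60% chance of a new low-grade event. It approaches 12 points only with 25% stopping, a figure from a long-term stroke study, combined with the most unfavourable of the other assumptions. The damage would be to a descriptive safety comparison in a pilot trial. The correction is still worth making because it costs almost nothing.

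**What to change.** Reconcile the three statements in section 1.2 to a single recording threshold. Apply it identically in both arms from enrolment to day 28, whatever the treatment status. Specifically:

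- state the threshold in all three places, including under Reporting of Serious Adverse Events, where none is given;
- make the post-withdrawal sentence refer to new AEs that meet that threshold;
- remove the start point tied to study drug, so that the window is defined for standard-care patients too;
- if low-grade events after withdrawal are wanted beyond the common threshold, list them separately and keep them out of the between-arm AE summary.

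Any single threshold removes the imbalance in the recording rule; which grade to use is for the sponsor to decide. The cost is wording in three places and one case-report-form rule, with no extra patients or procedures if the existing grade 3 threshold is kept. The small downside is that separately listed low-grade events leave the comparative table.

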- o Medical history
- o Physical examination will be performed as part of the routine care and will be abstracted from the medical record
- o Vital signs (blood pressure, heart rate, temperature) will be abstracted from the medical record
- o Electrocardiogram will be performed as part of the routine care and will be abstracted from the medical record
- o Labs: CBC, BMP, Coagulation profile, Ferritin, D-Dimer, CRP. will be collected as part of the routine care and will be abstracted from the medical record
- o Concomitant medications (starting from the time the patient signs the informed consent)
- o Collection of research samples:
 - Saliva, oral, nasal, and pharyngeal swabs, and sputum (if spontaneously producing sputum or intubated) for SARS-CoV-2 RNA will be collected at baseline day 0
- Randomize study participant through RedCap.

Treatment Period –Days 1 - 14 (Complete daily COVID Case report form – Appendix B: Module 2)

- Clinical assessment completed by Research Nurse. May be conducted by phone if the patient is discharged before 14 days.
 - Review of daily temperatures
 - Review of medication compliance
 - Adverse events

Protocol Title: ATTAC-19 – Aggrenox To Treat Acute Covid-19 Pro#2020001469

Rutgers, The State University of New Jersey [name]

- Record standard of care treatments and/or procedures prescribed
- Labs: At day 7 and day 14: we will abstract CBC, BMP, Coagulation profile, Ferritin, D-Dimer, CRP results from the medical record.

Collect research specimens:

- Saliva, oral, nasal, and pharyngeal swabs, and sputum (if spontaneously producing sputum or intubated) for SARS-CoV-2 RNA will be collected at day 7 and day 14 in a subset of patients.
- Urine samples will be collected on day 1 and day 14.

Treatment Period –Days 15 - 28 (Complete daily COVID Case report form – Appendix B: Module 2)

- Clinical assessment completed by Research Nurse. May be conducted by phone if the patient is discharged before 14 days.
 - Review of daily temperatures
 - Adverse events
 - Record standard of care treatments and/or procedures prescribed
 - COVID ordinal outcomes scale on day 28.

Discharge/ Death: Complete COVID Case report form –(Appendix B: Module 3)

Treatment Plan:

Participants will be randomized 1:1 to Aggrenox or standard treatment.

- Active Comparator: (Aggrenox (Dipyridamole ER 200mg/ Aspirin 25mg orally/enterally).

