Change (as compared to baseline on day 0) in composite COVID ordinal scale at day 15 Ordinal scale: 1) not hospitalized with resumption of normal activities; 2) not hospitalized, but unable to resume normal activities; 3) hospitalized, not requiring oxygen; 4) hospitalized, requiring oxygen; 5) hospitalized, requiring high-flow oxygen therapy, or noninvasive ventilation; 6) hospitalized, requiring invasive ventilation; 7) ventilation plus additional organ support such as vasopressors, renal replacement therapy and ECMO and 8) death.

Secondary endpoints:

- 1) all-cause mortality assessed on day 15 and day 28.
- 2) oxygen-free days through day 28.
- 3) invasive-ventilator-free days through day 28.

Protocol Title: ATTAC-19 – Aggrenox To Treat Acute Covid-19 Pro#2020001469

Rutgers, The State University of New Jersey [name]

- 4) ICU-free days through day 28.
- 5) hospital-free days through day 28.
- 6) increase in cycle threshold (Ct) of SARS-CoV-2 PCR test as an approximation of decline in viral load at days 7 and 15.
- 7) Change in the inflammatory markers D-dimer/ ferritin/ c-reactive protein at days 7 and 15 as compared to baseline on day 0.
- 8) thromboembolic complications including stroke at day 28.
- 9) Change (as compared to baseline on day 0) in COVID ordinal scale at day 28.
- 10) if feasible urine will be analysed for markers of tubular injury IL-18, kidney injury molecule-1 [KIM-1], neutrophil gelatinase-associated lipocalin [NGAL]), inflammation (monocyte chemoattractant protein-1 [MCP-1]), and repair (human cartilage glycoprotein-40 [YKL-40]

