1.5 Sample Size Justification

The sample size of 132 patients (66 patients in each arm) was estimated to provide 90% power to detect a relative between-group difference of 20% reduction in composite ordinal scale (from day 0 to day 15) with assumption of mean composite ordinal scale value of 4.5 ± 1.6 (yes- this is SD) at baseline (day 0) and two-sided P value of $0.05.^{25}$ For primary efficacy, we will do an intention-to-treat analysis and include all patients who have undergone randomization and will adjust for the minimization variables. We will analyze continuous measures by means of linear regression and present as mean differences. For binary outcomes, we will present data as risk ratios from a binomial regression model.

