1.8 Specimen Collection

Primary Specimen Collection

The research samples collected will be studied using standard laboratory assays for:

1. SARs-CoV-2 RNA

Types of Specimens:

- Saliva, oral, nasal, and pharyngeal swabs, and sputum (if spontaneously producing sputum or intubated) for SARS-CoV-2 RNA will be collected at baseline day 0, day 7 and day 14 in a subset of patients.
- Urine samples will be collected on day 1 and day 14.
- Annotation: Data to be annotated or associated with each specimen include participant ID (PID), date and time of collection, and specimen type. A PID will be assigned at the time of screening; at the time of specimen collection, all specimens collected will be labelled with the PID, date/time of collection, study timepoint, and specimen type. No identifiers will be included on the labels. These PIDs will be used to link the specimens with REDCap database containing the data collected from the EHR. All identifiers include name and date of birth matched to PID will be kept in a separate encrypted, password-protected electronic file that is accessible only by designated study personnel.
- Transport: All samples will be collected into sealed container(s) with de-identified PIDencoded labels and placed in a cooler. Samples will be transported to the hospital hematology and microbiology labs by trained personnel. The respiratory samples (saliva, swabs, sputum) will be processed in the [name] laboratory. Urine specimens will be transported by the study coordinator to a -80C freezer in the MSB A900 unit for temporary storage until analysis.
- Processing: Specimen processing will occur in accordance with approved Rutgers NJMS Institutional Biosafety Committee protocols.
- Storage: Urine will be stored at -80C in freezers in the MSB until processing and accessible by the study investigators and their laboratory personnel. Respiratory samples will be stored at -80C in the RBL, accessible by [name] and their laboratory personnel.
- Disposition: Analysis will occur at the end of the study/accrual period. Any unused specimens will be discarded upon study completion following appropriate biohazard disposal procedures by [name] laboratory personnel for the respective specimens.

B. Secondary Specimen Collection

N/A

Protocol Title: ATTAC-19 - Aggrenox To Treat Acute Covid-19 Pro#2020001469

Protocol Version 6 Date: 4/18/2021

7/21/2021

Rutgers, The State University of New Jersey [name]

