- 4. Lab test result pending plus a high clinical suspicion for SARS-CoV-2 (fever and cough for ≤ 7 days, bilateral pulmonary infiltrates on imaging or new hypoxemia with spO2 ≤94% on room air or no alternative explanation for respiratory symptoms).
- 5. Willing and able to provide consent or by authorized proxy.

Exclusion Criteria:

- 1. Pregnancy.
- 2. History of G-6PD deficiency.
- 3. Use of antiplatelet agents including inhibitor of P2Y12 ADP platelet receptors, phosphodiesterase inhibitors, and Glycoprotein IIB/IIIA inhibitors.
- 4. On therapeutic anticoagulation with coumadin, unfractionated heparin, enoxaparin (lovenox) and direct oral anticoagulants. (prophylactic anticoagulation is now standard of care and patients on prophylactic anticoagulation such as enoxaparin or unfractionated heparin, will be included in the study)
- 5. Vasodilatory shock.
- 6. Patient with known ongoing angina, recent myocardial infarction and sub-valvular aortic stenosis.
- 7. Active gastric or duodenal ulcer or any bleeding disorder or creatinine clearance < 10.
- 8. Hemoglobin <9 mg/dL, platelet count of <30,000 /mm³.
- 9. Acute respiratory infection for >10 days.
- 10. Known allergy/hypersensitivity to Dipyridamole and/or Aspirin.
- 11. Severe hepatic or renal insufficiency.
- 12. Uncontrolled hypertension defined as systolic > 180 mm Hg or diastolic > 100 mm Hg.
- 13. Patients with known allergy to NSAIDs
- 14. Patients enrolled in other non-standard of care clinical trials.

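### Secondary endpoint 6 is a mean difference in Ct, but the plan has no rule for a swab with no detectable RNA; both simple conventions shrink a true effect

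*Combined protocol and SAP*

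**What the plan says.** - **Endpoint.** Section 1.1 and part B (Endpoints) of Research Design and Methods both list secondary endpoint 6 as an "increase in cycle threshold (Ct) of SARS-CoV-2 PCR test as an approximation of decline in viral load at days 7 and 15".
- **Method.** Section 1.5, repeated in section 6.1, says: "We will analyze continuous measures by means of linear regression and present as mean differences". Nothing more specific is given for Ct.
- **Population.** The rule to keep every randomized patient is tied to the primary analysis: "For primary efficacy, we will do an intention-to-treat analysis and include all patients who have undergone randomization". No population is stated for endpoint 6.
- **Specimens.** Section 1.8 lists "Saliva, oral, nasal, and pharyngeal swabs, and sputum (if spontaneously producing sputum or intubated) for SARS-CoV-2 RNA". The condition in brackets applies to sputum. No section names the specimen that supplies the endpoint Ct, or requires it to be of the same type as at baseline.
- **Coverage.** The treatment-period procedures say "sputum (if spontaneously producing sputum or intubated) for SARS-CoV-2 RNA will be collected at day 7 and day 14 in a subset of patients". The size of the subset is not given, and day 14 sampling does not match the day 15 endpoint.
- **Not stated anywhere.** The assay's cut-off, the value or status of a not-detected result, and the handling of missing Ct.

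**The concern.** Ct rises as viral load falls, and it stops existing once the assay finds no RNA. A not-detected swab is therefore the most favourable result a patient can have, yet it gives linear regression no number to use. Whoever analyses the data must either leave the patient out or invent a value.

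Leaving patients out selects on the outcome. If Aggrenox speeds clearance, more patients leave the Aggrenox arm, and those who remain in the two arms look more alike than they should. Putting in the cut-off keeps the patients but caps their improvement.

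Section 1.2 offers antiviral action as part of the rationale, and endpoint 6 is the listed endpoint that addresses viral load. A real effect could be reported as small or absent. The choice would also be made in an open-label trial, after the results are known.

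A lesser gap is that the reference specimen is not named. Sputum becomes available when a patient is intubated, which is an event after randomization. An analyst who used whatever specimen was at hand could compare an upper-airway Ct with a sputum Ct.

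**Working it through.** **The plan's own figure.** The documents give no number for Ct. Their one calculation concerns the primary endpoint: difference 0.20 × 4.5 = 0.9, SD 1.6, two-sided 0.05, power 90%. Then n per arm = 2 × (1.6/0.9)² × (1.960 + 1.282)² = 66.4, rounded up to 67, or 134 in total. Power at 66 per arm is 89.8%. The stated 132 is reproduced within two patients. It neither supports nor weakens the point about Ct.

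**Inputs for Ct, all assumed.** Cut-off L = 40; SD of follow-up Ct σ = 6; control mean μ from 28 to 38; true shift δ of 2 or 3 cycles.

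**Formulas.** With a = (L − μ)/σ, and φ and Φ the standard normal density and distribution function:

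- proportion not detected = 1 − Φ(a)
- mean if not-detected is dropped = μ − σφ(a)/Φ(a)
- mean if not-detected is set to L = μΦ(a) − σφ(a) + L(1 − Φ(a))

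**Worked case, control mean 36, shift 3 (treated mean 39).**

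- Control: a = 0.667, φ = 0.3194, Φ = 0.7475. Not detected 25%. Dropped: 36 − 6 × 0.3194/0.7475 = 33.44. Set to 40: 26.91 − 1.92 + 10.10 = 35.09.
- Treated: a = 0.167, φ = 0.3934, Φ = 0.5662. Not detected 43%. Dropped: 39 − 6 × 0.3934/0.5662 = 34.83. Set to 40: 22.08 − 2.36 + 17.35 = 37.07.
- Difference if dropped: 1.39 of 3 cycles (46%). Difference if set to 40: 1.98 of 3 cycles (66%).

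**Range.**

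| Control mean Ct | Not detected, control vs treated (shift 3) | Kept if dropped, shift 3 | Kept if dropped, shift 2 | Kept if set to 40, shift 3 |
|---|---|---|---|---|
| 28 | 2% vs 7% | 83% | 85% | 96% |
| 30 | 5% vs 12% | 75% | 77% | 92% |
| 34 | 16% vs 31% | 56% | 58% | 77% |
| 36 | 25% vs 43% | 46% | 49% | 66% |
| 38 | 37% vs 57% | 38% | 40% | 53% |

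**Check with baseline adjustment.** A simulation with 400,000 patients per arm used a different model: baseline Ct 26 (SD 5), SD of change 6, cut-off 40, true effect 3.0.

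| Control rise in Ct | Not detected, control vs treated | Dropped | Set to 40 |
|---|---|---|---|
| 4 | 10% vs 18% | 2.3 (76%) | 2.6 (86%) |
| 8 | 22% vs 35% | 1.9 (64%) | 2.2 (72%) |
| 12 | 40% vs 55% | 1.5 (51%) | 1.6 (53%) |
| 16 | 60% vs 74% | 1.2 (39%) | 1.0 (33%) |

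Adjusting for baseline does not remove the shrinkage. Under the heaviest censoring tried, setting results to the cut-off did no better than dropping them. With no true effect, both conventions gave a difference of about 0, so the problem is a diluted effect and not a false positive.

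**Does a censored model repair it?** In 600 simulated trials (control mean 36, shift 3, SD 6, baseline correlation 0.4), the average estimate was 1.6 cycles with detected results only, 2.0 with not-detected set to 40, and 3.0 with a right-censored (Tobit) regression. The data were generated as normal, which favours that model.

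**The case against.** A reader might infer that the plan excludes patients who have cleared the virus. It does not say so. It is silent, and the shrinkage depends on how the silence is filled. That stands, and the point is worded accordingly. The silence still matters, because the two conventions most likely to be used with the stated method both shrink the estimate.

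A reader might also infer that a change of specimen removes responders. It does not. Saliva and the oral, nasal and pharyngeal swabs are listed without condition at every swab time, so a patient intubated after day 0 should still have a sample that matches baseline. A mismatch arises only if an analyst switches specimen, and its direction would be unknown. Naming the specimen is a clarification.

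The net direction of error in the trial cannot be claimed either. Ct can be missing through death, through discharge (of the clinical assessment: "May be conducted by phone if the patient is discharged before 14 days", with no swab route stated), or because baseline positivity was unconfirmed at entry ("Lab test result pending plus a high clinical suspicion for SARS-CoV-2"). These losses may act in other directions, and a censored model addresses none of them.

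The full sample ("The sample size of 132 patients (66 patients in each arm") is not the basis for power on Ct, because follow-up swabs come from a subset of unstated size. Power figures at 66 per arm therefore do not describe this endpoint.

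Finally, the documents give no clearance rate. With little censoring the loss is modest, as the first row of the range table shows. This is one of ten secondary endpoints in an exploratory pilot.

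**Conclusion.** The point holds in conditional form. The plan's only method for a continuous measure has no valid place for a not-detected swab. If such swabs are dropped, the difference is biased toward zero, and about 38% to 85% of a true shift of 2 to 3 cycles is kept for control mean Ct from 38 down to 28. If they are set to the cut-off, about 53% to 96% of a shift of 3 is kept over the same range. These figures rest on an assumed cut-off of 40, SD of 6 and normal Ct. The direction of this particular bias is secure for a drug that truly raises Ct; its size is not known. Nothing here touches the primary endpoint, so the change is advisable and not critical.

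**What to change.** In endpoint 6 and section 6.1:

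1. State the assay's cut-off. Analyse follow-up Ct with a regression that treats not-detected as right-censored at that cut-off, adjusted for baseline Ct.
2. Add a rank-based analysis, with not-detected ranked best, as a check on the normality assumption.
3. Report the proportion not detected by arm at each follow-up time.
4. As a secondary clarification, name one upper-airway specimen type, paired with its own baseline, as the source of the endpoint Ct. Report sputum separately, because its availability depends on intubation after randomization.

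The day 14 sampling and the day 15 endpoint also need to be reconciled. Ct missing through death, discharge or a pending baseline test needs its own statement.

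The cost is wording. Samples and assays stay the same, and section 1.8 places specimen analysis at the end of the accrual period, so the rule can be fixed before any follow-up Ct is seen. The small downside is that the censored model relies on normality, which item 2 is there to check.
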